13 T: [name]

14

15

16

17 **1 INTRODUCTION**

18 Idiopathic achalasia is a rare motility disorder of the oesophagus with an annual
19 incidence rate of 1 per 100,000 persons.¹ Achalasia is characterised by aperistalsis of
20 the oesophageal body and dysrelaxation of the lower oesophageal sphincter caused by
21 progressive destruction and degeneration of the neurons in the myenteric plexus. This
22 leads to subsequent retention of food and saliva in the oesophagus, resulting in the
23 typical symptoms of achalasia such as dysphagia, chest pain, regurgitation of
24 undigested food and weight loss. At the long term, incomplete oesophageal emptying
25 and reflux result in an increased risk for development of squamous cell carcinoma of the
26 oesophagus.^{1,2} The cause of the neuronal degeneration found in achalasia is unknown.³
27 Treatment of achalasia is focused on symptom relief, which is obtained by destroying the
28 occluding function of the spastic lower oesophageal sphincter. Usually, the first step is
29 endoscopic dilation of the lower oesophageal sphincter using a pneumatic balloon.^{4,5}
30 However, a disadvantage of this treatment is the high chance of symptom recurrence
31 which requires subsequent treatment sessions. Also, approximately 3% of the
32 endoscopic pneumodilations (PD) is complicated by a perforation, which is a potentially
33 life-threatening situation.⁶ When symptoms recur after endoscopic balloon dilation a
34 surgical myotomy can be considered. During a surgical myotomy the circular muscle
35 fibers of the lower oesophageal sphincter are cut laparoscopically and this results in a
36 lower recurrence rate than pneumodilation.⁷ However, this technique can also be
37 associated with severe complications, is more invasive and is more expensive as it
38 involves laparoscopic instrumentarium. Currently, endoscopic pneumodilation is the first
39 choice of treatment in patients with achalasia and surgical myotomy is generally
40 performed in case of symptom recurrence after initial pneumodilation.
41 Recently, per-oral endoscopic myotomy (POEM) has been introduced as an alternative
42 to surgical myotomy.⁸ The POEM technique is entirely endoscopic and is performed
43 under total anesthesia at the endoscopy suite. Using an endoscopic knife, an entry to
44 the submucosal space is made in the oesophagus and after creating a submucosal
45 tunnel towards the lower oesophageal sphincter the circular muscle layers are cut. At the
46 end of the procedure the mucosal opening is closed with clips. In our centre we have
47 now treated more than 10 patients successfully with POEM and we were able to confirm
48 the positive findings in symptom improvement and lower oesophageal sphincter
49 pressure reduction reported by the German and Japanese pioneers of the technique.^{8,9}

50 **2 HYPOTHESIS**

51 We hypothesize that POEM has a higher long-term efficacy than PD in treatment of
52 therapy-naive patients with idiopathic achalasia.

53

54 **3 AIM**

55 To compare the efficacy of POEM to the efficacy of PD as the initial treatment of
56 symptomatic idiopathic achalasia.

57

58 **4 STUDY DESIGN**

59 This is a multi-centre randomised clinical trial in which a new treatment (POEM) will be
60 compared to the gold standard (PD). The primary endpoint will be measured at two
61 years after treatment and follow up will be extended up to five years.

62

63 **5 PRIMARY OUTCOME**

- 64 • Treatment success, defined as:
- 65 ○ An Eckardt score of 3 or less
 - 66 ○ The absence of the need for endoscopic or surgical retreatment in the
67 period between the first treatment session (first and optional second
68 dilation within first 3 months) and the endpoint
 - 69 ○ The absence of severe complications associated with treatment.

70

71 **6 SECONDARY OUTCOMES**

- 72 • Quality of life and achalasia-specific quality of life
- 73 • Stasis in the oesophagus, measured with a timed barium oesophagogram
- 74 • Presence of reflux symptoms, reflux oesophagitis and excessive oesophageal
75 acid exposure
- 76 • Lower oesophageal sphincter pressure and integrative relaxation pressure
77 (IRP4), as measured with high-resolution manometry
- 78 • Complications of the treatment, defined as any unwanted events that arise
79 following treatment and/or that are secondary to the treatment. Complications are
80 classified as “severe” when these result in admission > 24 hours or prolongation
81 of an already planned admission of >24 hours, admission to a medium or

82 intensive care unit, additional endoscopic procedures, or blood transfusion or
83 death. Other complications are classified as “mild”.

- 84 • The need for endoscopic or surgical retreatment after the initial treatment session

85

86 **7 POPULATION**

87 **7.1** *Subjects*

88 Adult patients with symptomatic idiopathic achalasia that have not undergone
89 endoscopic or surgical treatment for achalasia before.

90

91 **7.2** *Inclusion criteria:*

- 92 • Presence of achalasia, as shown on oesophageal manometry
- 93 • Eckardt score > 3
- 94 • Age between 18-80 years
- 95 • Signed written informed consent
- 96 • ASA class I or II

97

98 **7.3** *Exclusion criteria*

- 99 • Previous endoscopic or surgical treatment for achalasia, except botulinum toxin
100 injections
- 101 • Previous surgery of the stomach or oesophagus
- 102 • Known coagulopathy
- 103 • Presence of liver cirrhosis and/or oesophageal varices
- 104 • Presence of eosinophilic oesophagitis
- 105 • Presence of Barrett’s oesophagus
- 106 • Pregnancy at time of treatment
- 107 • Presence of a stricture of the oesophagus
- 108 • Presence of malignant or premalignant oesophageal lesions
- 109 • Presence of an extensive, tortuous dilated oesophageal body (S-shape)
- 110 • Presence of a diverticula in the distal oesophagus

111

112

113 **8 METHODS**

114 **8.1** *Study protocol*

115 **Study enrolment and randomisation**

116 In the AMC, patients will be approached that visit the outpatient clinic of the Motility
117 centre of the Gastroenterology department. Patients should be diagnosed with achalasia
118 by manometry using the predefined manometric criteria and have not undergo surgical
119 or endoscopic treatment for achalasia before. Eligible patients will be given a verbal
120 explanation of the study. Each patient will receive a patient information brochure about
121 the study and an informed consent form for participation. Patients will be given sufficient
122 time to read the information and ask questions. Before any study procedures or
123 randomisation are initiated the patient must sign the informed consent form.

124

125 There is no time frame for the randomisation. When participants are recruited for the
126 study the time to consider participation in the study is unlimited. Before randomisation
127 the patient must have signed the informed consent form. Randomisation will be done
128 using a web-based program and is stratified for each centre, so that the number of
129 patients treated with POEM or pneumatic dilation is similar for each centre. The
130 randomisation for the two treatments will be 1:1.

131

132 **Baseline**

[figure not shown]
133 At baseline, patients will undergo oesophageal manometry, timed barium
134 oesophagography and upper endoscopy. A venous blood withdrawal is performed to
135 screen for abnormalities in blood count, chemistry lab and clotting. If any of these tests
136 have been performed within the last 6 months and of high quality (at the discretion of the
137 investigator) it is not required to repeat this. Questionnaires regarding symptoms and
138 quality of life (see 8.4) are filled in by the patients.

139

140 **General follow up**

141 Patients that are randomised to endoscopic balloon dilation will be asked to fill in an
142 Eckardt score three weeks after the dilation. If this score is still more than 3, they will be
143 scheduled to undergo a second pneumatic dilation, but now using a 35 mm balloon
144 (figure 1). Manometry is performed if the Eckardt score is 3 or less. If the manometry

145 shows an IRP of more than 10, patients will also undergo a second pneumatic dilation
 146 (with a 35 mm balloon).
 147 Manometry and timed barium oesophagography are performed and questionnaires are
 148 filled in all patients 3 months after treatment and at 1, 2 and 5 years after treatment.
 149 Twenty-four hour pH-impedance monitoring is performed one year after treatment to
 150 evaluate oesophageal acid exposure. Upper endoscopy is performed at 1, 2 and 5 years
 151 after treatment.
 152
 153
 154

155
 156 *Figure 1 Treatment algorithm used in this study*
 157

158
 159
 160
 161
 162
 163

	Baseline	3 weeks*	3 months	1 year	2 years	5 years
Blood count, chemistry, clotting	X					
Questionnaires	X	Eckardt*	X	X	X	X
Timed barium oesophagography	X		X	X	X	X
Manometry	X	If Eckardt >3*	X	X	X	X
Upper endoscopy	X			X	X	X
pH-impedance monitoring				X		

164

165

Table 1 Schedule of baseline and follow-up examinations; * only for patients randomised to balloon dilation

166

167

168 **8.2 Pneumodilation (PD)**

169 In this study pneumodilation will only be performed by experienced endoscopists, that
170 have performed over 20 pneumodilation procedures. Patients are asked to use clear
171 fluids only starting 24 hours before the procedure and nil per mouth starting 8 hours
172 before the procedure. Under fluoroscopic guidance a Rigiflex balloon (Boston Scientific)
173 is positioned at the esophagogastric junction and dilated at a pressure of 5 PSI, followed
174 by dilation with 8 PSI for one minute (Figure 2).^{8,10} The initial pneumatic dilation is
175 performed using a 30-mm balloon. Three weeks later the symptoms of patients are
176 evaluated using the Eckardt score. If the Eckardt score is still higher than 3, a
177 subsequent dilation with a 35-mm balloon is scheduled. If the Eckardt score is less than
178 3 a subsequent high-resolution manometry is scheduled. If this shows an integrative
179 relaxation pressure (IRP4) of more than 10 mmHg, a subsequent dilation with a 35-mm
180 balloon is scheduled as well. In total, patients will thus undergo one or two pneumatic
181 dilations in the first 6 weeks. A second dilation within this 6 week period is not
182 considered a failure but considered part of the regular treatment. PPI are taken orally in
183 a single daily dose for two weeks after each dilation.

[figure not shown]

Figure 2 Schematic outline of a pneumatic balloon dilation

[figure not shown]
184
185
186
187

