420 advisory capacity to monitor participant safety and evaluate the efficacy and the overall
421 conduct of the study. The DSMB will be informed about adverse events and serious
422 adverse events that occur during the study. The advice(s) of the DSMB, in case it
423 influences the set-up of the study, will be notified upon receipt by the sponsor to the
424 METC that approved the protocol. With this notification a statement will be included
425 indicating whether the advice will be followed.

426

427 **10 STATISTICAL ANALYSIS AND RANDOMISATION**

428 We aim to perform an intention to treat analysis. After testing for normality, pairwise
429 comparisons will be performed between the two treatment arms for all primary and
430 secondary outcomes. Categorical variables will be compared using the Chi-square test.
431 The success rates of the two treatment arms will be compared using log-rank tests on
432 Kaplan-Meier estimates.

433 Randomisation will be done using a web-based online available program and is stratified
434 for each participating centre.

435

436 **11 SAMPLE SIZE ANALYSIS**

437 Recently reported complication free success rate of a two step PD strategy is 68% at
438 two years.⁶ Long term outcome data of POEM is lacking but at three months a success
439 rate of 94% has been described.⁹ Assuming success rates of 70% for PD and 90% for
440 POEM after two years, we estimated that with 62 patients in each group, the study would
441 have 80% power to detect a significant difference in success rate between PD and

442 POEM with a two-sided alpha level of 0.05. To cope with an estimated 5% loss to follow-
443 up, we aim to enrol 130 patients.

444

445 **12 PRIVACY**

446 The data of the subjects are coded in order of participation. The code and the data are
447 stored in different locations. The code can only be seen by the investigators. Qualified
448 authorities can get insight in code and data, but only when accompanied by the
449 investigators. Data will be stored 20 years after closure of the trial.

450

451 **13 ETHICAL CONSIDERATION**

452 The protocol of this study will be submitted to the Medical Ethical Committee of the
453 Academic Medical Center and will not start before formal approval has been granted.
454 Participants will be given oral and written explanation about the study, before they give
455 written informed consent. Subjects are allowed to withdraw informed consent without
456 providing arguments.

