631 the first year of follow-up will be retreated with a pneumodilation using a 40 mm rigiflex
632 balloon. In case subjects fail more than 1 year after the initial pneumodilations they will
633 be retreated with a pneumodilation using a 35 mm and 40 mm rigiflex balloon.

[figure not shown]
634 This is in contrast with the previous versions of the protocol concerning treatment failure
635 that stated that these patients should be subsequently treated with a POEM procedure.
636 The reason to retreat the patients first with a third pneumodilation of 40 mm is that the
637 optimal pneumodilation protocol is used in this way. After the additional
638 pneumodilation(s) symptoms should be evaluated by the Eckardt score. In case the
639 Eckardt is >3 the patient can be scheduled for a POEM procedure.

640

641 **Follow-up of treatment failures**

642 In principal, study subjects that failed on the initial treatment (2x pneumodilation or
643 POEM) achieved the primary endpoint at that moment. For these patients page 49,
644 study termination, of the CRF should be filled in.

645 It is very important to continue to collect the data of the treatment failures because sub-
646 analyses of these data can be performed at the end of the study. Therefore, follow up
647 will be the same as the study protocol; follow-up should be scheduled with regard to the
648 date of the initial treatment.

649
650
651
652
653
654
655

Treatment failure algorithm

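### A second pneumodilation is exempt from failure up to 3 months in Section 5 but only up to 6 weeks in Section 8.2, so one done in between can be scored either way on the primary endpoint

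*Protocol*

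**What the plan says.** Section 5 (Primary outcome) makes freedom from retreatment one of three components of treatment success: "The absence of the need for endoscopic or surgical retreatment in the" interval from the first treatment session to the endpoint. For PD, that session covers the first and an optional second "dilation within first 3 months) and the endpoint".

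Section 8.2 (Pneumodilation) concludes that patients will have one or two "dilations in the first 6 weeks. A second dilation within this 6 week period is not", and the sentence continues "considered a failure but considered part of the regular treatment. PPI are taken orally in" (the last words open the next sentence, on another subject).

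Section 8.1 (General follow up) fixes the check that leads to a second dilation. Patients complete an "Eckardt score three weeks after the dilation. If this score is still more than 3, they will be" scheduled for the larger balloon. Those whose score is no longer above 3 have manometry and are also dilated again if the IRP is above 10. No latest date is given for the second dilation.

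The addendum (Section 16) makes an Eckardt score above 3 within 2 years, or an indication for retreatment, a failure when it comes after the initial treatment. Its only description of that treatment for PD is in the follow-up paragraph: "In principal, study subjects that failed on the initial treatment (2x pneumodilation or" POEM. It states no window.

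**The concern.** Sections 5 and 8.2 answer the same question: when does a second dilation stop being part of initial treatment and become retreatment? They give different limits. A second dilation in, say, week 8 lies inside the initial session under Section 5 and outside the exempt period under Section 8.2.

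The answer feeds the primary endpoint, the time of failure in the Kaplan-Meier comparison (Section 10), and the secondary outcome on retreatment after the initial session (Section 6). The window exists only for PD, so an error in applying it does not cancel between arms. Sites also act on the definition, because the addendum tells them to complete the study-termination page of the case report form at failure. Two centres could therefore record identical patients differently. If the choice is left until the data are in hand, it will be made when its effect on the result can be seen.

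**Working it through.** **1. The passages side by side**

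| Place | Limit on an exempt second dilation | Status of a later one |
|---|---|---|
| Section 5 | 3 months (about 13 weeks) | retreatment, hence failure |
| Section 8.2 | 6 weeks | not stated; failure by implication, because the exemption is confined to that period and Section 5 counts retreatment as failure |
| Section 8.1 | none; the check is at 3 weeks | not stated |
| Addendum | none; two pneumodilations | failure if retreatment is indicated after the initial treatment |

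All of these are current text. The disputed interval is about 13 − 6 = 7 weeks. The addendum does not settle it, because it relies on the term that the other two sections define differently.

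**2. How a patient can fall in the gap**

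- Delay. The check is at week 3. Some patients then need manometry before the decision, and 6 − 3 = 3 weeks remain to schedule the dilation. A second step triggered on time but done in week 7 is exempt under Section 5 and not under Section 8.2.
- A later second dilation, if Section 5's 3 months is read literally and not tied to the 3-week check.

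The date that counts also matters. The endpoint is worded as the need for retreatment, whereas both windows are worded around the dilation itself. If the date of indication governed, a second step indicated at week 3 would be exempt under either limit.

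**3. The plan's own sample size**

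Inputs from Section 11: "Assuming success rates of 70% for PD and 90% for" POEM, two-sided alpha 0.05, power 80%, 62 per group. With the pooled-variance formula, no continuity correction and p̄ = 0.80:

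n = [1.96·√(2·0.80·0.20) + 0.8416·√(0.70·0.30 + 0.90·0.10)]² / 0.20² = (1.109 + 0.461)² / 0.04 = 61.6, so 62 per group.

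Power at 62 per group is 80.3%. The sample size reproduces and is not in question.

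**4. Size of the ambiguity**

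One PD patient is 1/62 = 1.6 points. Let f be the share of PD patients who have their second dilation in the gap and are otherwise successes. Then PD success under the 6-week limit equals PD success under the 3-month limit minus f. The documents do not give f, so 0 to 10% is an assumption. They also do not say which limit the 70% corresponds to, so both cases are shown. Power for comparing two proportions at 62 per group, with POEM at 90%, is

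Φ{[|Δ|·√62 − 1.96·√(2p̄(1−p̄))] / √(p₁q₁ + p₂q₂)}.

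For 65% v 90%: (1.969 − 1.157)/0.563 = 1.44, which gives 92.5%.

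| f | Patients of 62 | 70% holds under 3 months: PD under 6 weeks (power) | 70% holds under 6 weeks: PD under 3 months (power) |
|---|---|---|---|
| 0% | 0 | 70% (80.3%) | 70% (80.3%) |
| 2% | 1.2 | 68% (86.2%) | 72% (72.9%) |
| 5% | 3.1 | 65% (92.5%) | 75% (59.6%) |
| 10% | 6.2 | 60% (97.8%) | 80% (34.3%) |

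The direction is fixed: the 6-week limit can only lower PD success relative to the 3-month limit, and so can only widen the difference in favour of POEM.

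**The case against.** The strongest reply is that there is no true contradiction. Six weeks lies within 3 months, so both sections exempt a second dilation up to week 6. Section 8.2 never says that a later one is a failure, and its 6 weeks may only describe the expected timetable after a 3-week check. Section 5 is the endpoint definition and might be taken to prevail. Part of this stands: failure after week 6 is an inference. But Section 8.2 itself speaks of failure and ties the exemption to its 6-week period, and nothing says which section takes precedence.

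A reader might also infer that the 3-month limit lets a PD patient pass the 3-week check, relapse at week 8 to 12, be dilated again and still be a success. The documents do not support this as the main case. The only stated triggers for a second dilation come from the 3-week check, and no re-dilation rule is attached to the 3-month visit. The addendum arguably makes a later Eckardt score above 3 a failure under either window.

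Nor is it an error that POEM has no matching window. PD is defined as a two-step strategy, and Section 11 draws on the reported success of such a strategy.

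Finally, the treatment and failure algorithms are figures that are not shown here, and an SAP may exist. Either might state a window, but the two text passages would still disagree.

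**Conclusion.** The inconsistency is real and lies in the definition of the primary endpoint. A second dilation between week 6 and month 3 is exempt under Section 5 and, by implication, a retreatment failure under Section 8.2. Neither Section 8.1 nor the addendum decides between them. Only the PD arm is affected, at about 1.6 points for each such patient who is otherwise a success.

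The total size is unknown. It is zero if every second dilation follows promptly on the 3-week check, and 2 to 10 points if 2% to 10% of PD patients fall in the gap. Those shares are illustrations. It would be tempting to take the 5% row and say that a quarter of the planned 20-point effect is at risk (5/20), but no figure in the protocol supports 5%, and it requires every affected patient to be otherwise a success at two years. The power figures show sensitivity and are not evidence that 62 per group is wrong.

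**What to change.** Reconcile the passages:

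- State one window in Section 5, Section 8.2 and the addendum, chosen without sight of outcome data by arm. Which window is right is for the investigators; this review takes no position.
- Say whether the window runs to the date the second dilation is indicated or the date it is performed.
- State that a dilation outside the window counts as a failure on the primary endpoint.
- Name the other window as a sensitivity analysis, using the dilation dates, and report how many PD patients change status.

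The cost is about a sentence in each of three places and one extra analysis. No new assessment is needed, provided that the case report form, which is not shown, records the dates of indication and dilation. That should be confirmed when the amendment is written.

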220 So far there is limited information about the complications related to the POEM
221 procedure because it is a relative new procedure and long-term follow-up is not yet
222 available. Serious adverse events are not described in the previous studies that
223 performed POEM. The main preoperative complications that are described are
224 subcutaneous emphysema, pneumoperitoneum and pneumothorax. Transmural
225 openings into the mediastinum and into the peritoneal cavity caused emphysema,
226 pneumoperitoneum and pneumothorax. During POEM the inner circular muscle layer is
227 separated from the outer longitudinal muscle layer, leaving the longitudinal muscles
228 intact.⁹ The longitudinal muscle fibers are extremely thin, so minor damage can lead to
229 transmural dissections into the mediastinum and peritoneal cavity.

230 Subcutaneous emphysema was treated conservatively and in all cases the emphysema
231 resolved spontaneously in 2-3 days after surgery. The treatment of the
232 pneumoperitoneum occurred in all patients during the operation. A needle or canula of
233 18G was placed in the abdominal wall which gave directly relieve.^{8,9} A pneumothorax
234 was a rare complication and in all cases thoracic drainage was administered during the
235 operation which gave immediately relieve. Other described rare complications
236 preoperatively were a minor bleeding, controlled by endoscopic coagulation, and small
237 perforations which were clipped.

238 Postoperative complications were rare. One article described pneumothorax as an
239 important postoperatively complication.¹² The treatment was in most patients
240 conservatively and in some patients a thoracic drainage was administered, dependent
241 on the lung compression volume. An uncommon postoperative complication was a
242 delayed hemorrhage, one day after the operation. This occurred in one patient and was
243 probably caused by a bleeding in the submucosal tunnel. A three-cavity tube was placed
244 by endoscopy into the stomach and lower part of the esophagus to compress the
245 bleeding. After four days the tube was removed without further complications. Another
246 rare complication was a superficial ulcer (Forrest III) at the cardia that was detected with
247 a control endoscopy two days after POEM. This was only seen in one patient. The
248 patient had to continue PPIs and the hospital stay was extended. The control endoscopy
249 7 days after the procedure showed healing of the ulcer.

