357 In accordance to section 10, subsection 1, of the WMO, the investigator will inform the
358 subjects and the reviewing accredited METC if anything occurs, on the basis of which it
359 appears that the disadvantages of participation may be significantly greater than was
360 foreseen in the research proposal. The study will be suspended pending further review
361 by the accredited METC, except insofar as suspension would jeopardise the subjects'
362 health. The investigator will take care that all subjects are kept informed.

363

364 **9.2** *Adverse and serious adverse events*

365 Pneumodilation is a safe and regularly performed procedure for patients with achalasia.
366 In this study the procedure will be performed by experienced endoscopists, that have
367 performed over 20 pneumodilations. Complications due to a pneumodilation are rare and
368 the main complication is an oesophageal perforation. The treatment of a perforation is
369 frequently conservatively, total restriction of food and drinks and intravenous antibiotic
370 therapy. In some cases surgery is needed. The incidence of a perforation during
371 pneumodilation is approximately 3%.⁶

372 POEM is a relative new procedure in the treatment of achalasia. In Germany and Japan
373 the first POEM procedures were performed and in the AMC so far 10 patients are
374 treated with POEM. Because the follow-up of the first patients is only 3-5 months,
375 nothing is known about long-term complications or efficacy. Major complications that can
376 occur during the procedure are a bleeding or oesophageal perforation. Treatment can
377 directly be performed during the procedure by clipping the bleeding or perforation. In

378 some cases a surgical procedure can be needed. Furthermore POEM can be
379 complicated by minor complications, like pneumoperitoneum and postoperative
380 subcutaneous emphysema. Pneumoperitoneum can be relieved by a puncture of the
381 abdominal wall using an 18-gauge needle during the procedure. Postoperative
382 subcutaneous emphysema is usually self-limiting and additional treatment is not needed.
383 So far the only complications that occurred in the treated patients of the AMC were a
384 minor bleeding that was stopped during the procedure and one patient developed a
385 pneumoperitoneum which relieved by a puncture of the abdominal wall using an 18-
386 gauge needle during the procedure.

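### Section 6 makes an additional endoscopic procedure a severe complication but not a chest drain, and the complication part of failure is worded three ways with SAE undefined

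*Protocol*

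**What the plan says.** Protocol section 5 makes treatment success depend on three conditions, the third being "The absence of severe complications associated with treatment". Section 6 supplies the grading. Complications are severe "when these result in admission > 24 hours or prolongation" "of an already planned admission of >24 hours, admission to a medium or" "intensive care unit, additional endoscopic procedures, or blood transfusion or" death. The rule then closes with a default: "Other complications are classified as" mild. Neither thoracic drainage nor surgery is named.

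Section 8.3.1 reports that during POEM a pneumothorax "was a rare complication and in all cases thoracic drainage was administered during the" operation, with immediate relief. It also reports postoperative pneumothorax, drained in some patients. Section 8.3 plans an overnight stay for POEM, with discharge the day after the procedure. Section 9.2 says that surgery may be needed after a POEM complication and after a PD perforation. It gives pneumoperitoneum and subcutaneous emphysema as examples of minor POEM complications; pneumothorax is not among them.

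The complication component is worded differently elsewhere. The second section numbered 8.9 (Premature termination of the study) sets SAEs beside severe complications as if they were the same thing, and applies a 10% limit to SAEs. The addendum (section 16) makes a treatment-related SAE a failure. The Protocol does not define SAE.

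**The concern.** The section 6 list decides who fails the third part of the primary outcome. It is a complete rule with a default, so it leaves no gap for later documents to fill. It treats two kinds of extra intervention unequally: a complication that leads to another endoscopic procedure is severe on that ground alone, while one that leads to a chest drain is severe only if something else on the list also happens.

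The case that falls through is one the Protocol itself describes, and only for POEM. POEM is the new treatment and the one hypothesised to be better, so a definition that can drop a POEM complication from the failure count should be settled before outcomes are known. If the 10% SAE limit uses the same list, the gap reaches safety monitoring too. The three wordings add a second problem: the primary-endpoint status of such a patient depends on which section is applied.

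**Working it through.** **1. The case run through section 6.** Take a pneumothorax drained during POEM, with relief at once and discharge less than 24 hours late.

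| Trigger in section 6 | Met? |
|---|---|
| Admission or prolongation of more than 24 h | No |
| Medium or intensive care | No |
| Additional endoscopic procedure | No |
| Transfusion or death | No |
| Default | Mild |

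Under section 5 this patient is a success if the Eckardt score is 3 or less and there is no retreatment.

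**2. What the list already catches.** Surgery, and many drains placed after the procedure, will usually bring a stay prolonged by more than 24 hours or higher care. Those events are severe already, in either arm. The gap is mainly drainage during the procedure with timely discharge.

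**3. Direction.** Drained pneumothorax is described only for POEM. The main PD complication is perforation, which section 9.2 says is often managed by withholding food and drink and giving intravenous antibiotics. That would normally meet the admission trigger. The identified case therefore favours POEM.

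**4. Size.** The plan's own figure reproduces. For 70% against 90%, two-sided alpha 0.05 and 80% power, with pooled variance:

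n = [1.960 × √(2 × 0.80 × 0.20) + 0.842 × √(0.70 × 0.30 + 0.90 × 0.10)]² / 0.20² = (1.109 + 0.461)² / 0.04 = 61.6, so 62 per arm.

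Power at 62 per arm is 80.3%. Inflating 124 for 5% loss gives 131, against 130 stated.

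With 130 enrolled 1:1, each arm has 65, so one reclassified patient moves POEM success by 1/65 = 1.5 points. The Protocol gives no rate for the event. As an illustration, suppose a share x of POEM patients would move from success to failure, with PD held at 70%, 62 analysed per arm, and 90% being the POEM rate under the present list:

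| Assumed x | Patients of 65 | POEM success | Power at 62 per arm |
|---|---|---|---|
| 0% | 0 | 90% | 80.3% |
| 1% | 0.65 | 89% | 75.2% |
| 2% | 1.3 | 88% | 69.6% |
| 3% | 1.95 | 87% | 63.7% |

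The table shows sensitivity only. The values of x are assumptions, and section 11 does not tie the 90% to any complication definition.

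For the SAE limit, the first review after 20 inclusions has about 10 patients per arm. One event is 10% and two are 20%, so a single reclassification can decide whether 10% is exceeded, if that limit counts the section 6 list.

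**5. The three wordings side by side.**

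- Section 5, graded by section 6: the drained patient above is a success.
- Section 8.9 (Premature termination): if SAE means severe complication, the patient is not counted; if SAE is wider, the patient may be.
- Addendum: the patient is a failure if the drained pneumothorax is called an SAE, and otherwise a success.

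Usage in section 8.3.1 does not settle the meaning. It says that earlier POEM studies described no serious adverse events. It then reports a delayed haemorrhage treated with a tube placed by endoscopy and left for four days, and an ulcer that lengthened the hospital stay. The haemorrhage meets the section 6 trigger of an additional endoscopic procedure. So an event can be severe under section 6 and yet not serious as section 8.3.1 uses the word, and the two terms cannot be taken as equal.

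**The case against.** The strongest reply is that section 6 grades mainly by consequence, and that an event resolved during the operation without consequence is deliberately mild. Section 8.3.1 appears to support this, since it reports no serious adverse events and also reports drained pneumothorax. The support is weak, because the same section also leaves the haemorrhage and the ulcer outside the serious category. Section 9.2 does not list pneumothorax among its minor examples either, so nothing shows that the omission was intended. The reply does have force in one respect: counting a drain but not needle relief of pneumoperitoneum is a judgement about severity. It has to be written down, and it cannot be deduced from the text.

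A second reply is that the safety information is not lost. Complications of both grades are a secondary outcome, all adverse events are recorded, and the DSMB is informed of them. That stands, but it does not change who counts as a primary-endpoint success.

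Four stronger readings are tempting, and the documents do not support them:

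- *Surgery and chest drains are exempt.* Most will meet an admission or higher-care trigger.
- *Only POEM failures are removed.* Section 9.2 foresees surgery in both arms; only the drained-pneumothorax case is specific to POEM.
- *Any check endoscopy is severe while any drain is mild.* An endoscopy counts only if a complication leads to it, which excludes the scheduled follow-up endoscopies. A drain is mild only if no other trigger applies.
- *The primary comparison is materially biased.* No rate is given, the event is called rare, and section 8.3.2 reports no pneumothorax in the centre's own series of more than 10 patients.

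**Conclusion.** The point holds in a narrow form. As written, a pneumothorax drained during POEM that meets no other trigger is mild and can be scored as a success, whereas a complication leading to an additional endoscopic procedure cannot. The inequality favours POEM. Its effect cannot be derived from the documents and is probably small: each patient is about 1.5 points of POEM success with 65 per arm, and the event must be drained, free of every listed trigger, and otherwise a two-year success. The power figures rest on assumed rates and on reading the planning 90% as the rate under the present list.

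The inconsistency between section 5, section 8.9 and the addendum does not depend on any rate. With SAE undefined, the complication component of failure is not fixed, and the same patient can be classified in opposite ways.

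**What to change.** Use one complication definition for section 5, section 8.9 (Premature termination) and the addendum, placed in section 6 and referred to from the other three places. If SAE is kept as a separate term for reporting, define it and say that it does not determine the primary endpoint.

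In section 6, put unplanned invasive non-endoscopic interventions (thoracic drainage, surgery) on the same footing as additional endoscopic procedures. State in the same sentence that needle relief of pneumoperitoneum, which section 9.2 treats as minor, is not counted.

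This changes how outcomes are classified and leaves patient care as it is. The cost is a sentence in section 6, three cross-references and a matching line on the complication form. The downside is that the POEM failure and SAE counts may become slightly less favourable.
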